
A.2.6. Project 6 Harmonization Project

The goal of the Harmonization Project is to develop and expand innovative measurement methods related to harmonization of delirium measures, outcomes, and predictors for clinical studies and treatment trials, and to refine measures of delirium diagnosis and severity in patients with all stages of dementia. For this project, we will receive de-identified data and will share de-identified SAGES data for harmonization purposes. No HIPAA data will be shared or received. We will only share de-identified data of participants who indicated in the consent form that they agree to the data sharing. This project is part of the NIA R33 grant: "Advanced-Stage Development and Utilization of the NIDUS Research Infrastructure to Advance Interdisciplinary Aging Research in Delirium." NIDUS (Network for Investigation of Delirium: Unifying Scientists) is a collaborative delirium network which proposes data harmonization across datasets to advance research. We have not yet identified the studies from which

de-identified data will be received nor with whom we will share the de-identified SAGES data. We will inform the IRB as soon as we know with whom we will share data and from whom we will receive data. Since no HIPAA data will be shared, we will be requesting IRB waivers for these harmonization studies.

A.2.7. Natural language processing (NLP) Project

Using deep natural language processing (NLP), we will review SAGES I and SAGES II medical charts from patients' index hospitalization from both BIDMC and BWH, to determine the rate of delirium. We will first conduct a pilot study with N=32 pilot delirium positive cases (by CAM assessment) to test potential delirium terms and narrow the listing to gain high sensitivity (true positive), that is, terms that help us identify who truly has delirium with high frequency. Once we identified the search terms with the best sensitivity, we will use NLP with all medical charts of the SAGES I and II cohorts. This NLP method will support our chart abstraction procedures described under A.4.10.5. Only participants who provided written consent to abstract their medical charts will be included.

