A.3.1. SAGES I Cohort (N=560): Eligibility criteria included for initial enrollment: 1) age 70 years and older; 2) English speaking; 3) scheduled to undergo elective surgery; 4) scheduled at least 6 days prior to surgery to allow adequate time for the baseline assessment; 5) anticipated length of stay of at least 2 days; 6) planned general or regional anesthesia; and 7) living within 40 miles from study site. Eligible surgical procedures were: total hip or knee replacement, lumbar, cervical, or sacral laminectomy, lower extremity arterial bypass surgery, open abdominal aortic aneurysm repair, or colectomy. Exclusion criteria included: 1) evidence of dementia (dementia diagnosis, use of dementia drugs, or score <69 or education-adjusted equivalent on baseline Modified Mini-Mental State Test⁵³ 2) active delirium on initial cognitive testing: 3) hospitalization within 3 months prior to enrollment to minimize risk of recent delirium; 4) terminal condition with life expectancy < 6 months including terminal diagnoses such as metastatic cancer, pancreatic cancer, or receiving palliative care; 5) inability to perform cognitive tests due to legal blindness or severe deafness; 6) history of schizophrenia or psychosis; 7) current chemotherapy due to patient time burden; 8) documented history of alcohol abuse or withdrawal within last 6 months, and/or reporting more than 5 (4) drinks per day for men (women); 9) and inability to pass an assessment for capacity to provide informed consent. Initially 560 patients were enrolled; 6 patients were excluded due to baseline dementia. We will continue follow-up interviews with this cohort under the existing IRB protocol (2009P-000262).

A.3.2. SAGES I SELECT Sample Sub-group (N=148). A subset of selected participants from SAGES I will be invited to participate in lumbar puncture or amyloid-PET, MRI and Transcranial Magnetic Stimulation (TMS) procedures based on their delirium status. Delirium is defined by fulfillment of the Confusion Assessment Method¹ or chart criteria.⁵⁴ We will invite all SAGES I participants who developed delirium during the index hospitalization to participate, and we will enroll 74 participants into this subgroup. Next, we will enroll a sample of 74 patients who did not develop delirium or sub-

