The rationale for using machine learning, and the lasso, is that the most commonly used alternative -- stepwise variable selection using regression models¹⁰⁹ -- have long been recognized to have validity issues, including that the models are overly optimistic, predictors do not replicate in other data sets, and the interpretation of effects is clouded due to multicollinearity.¹¹⁰ Machine learning attempts to overcome this through the use of resampling strategies (analogous to the bootstrap, but including random sampling among predictors and observations over an arbitrarily large number of resampling replicates) and flexibility in functional forms and inclusions of higher order interactions. The lasso is motivated by a similar goal but invokes a fundamentally different strategy. The lasso works within a generalized linear regression framework by applying a constraint to the value of the sum of the absolute value of the coefficients, and effectively shrinks estimates of unimportant predictors towards 0. The lasso is well suited to identifying important predictors when a small number of truly important predictors are available within a large sample of noisy predictors. Both machine learning and the lasso are suited for situations where the ratio of predictors is high relative to the number of observations, as is the case in our study. We will use a 67% sample of our observations for model development and the set-aside 33% sample will be used for model testing. The model development sample will include 90 delirious and 285 non-delirious, and the remaining 44 delirious and 141 nondelirious SAGES I participants will constitute the model testing sample. Models will be characterized using data from the testing sample in terms of accuracy, focusing on the root mean squared error (RMSE), but also looking at the overall (pseudo) *r*-squared. The RMSE, a measure of predictive accuracy, is the square root of the mean difference between model-implied (given predictors) and slope. Model fit and replicability are our measures of success for this Aim.

Aim 2a. Analysis Approach. As with Aim 1b we will use machine learning and lasso-constrained linear regression models as described for Aim 1a with (i) delirium and (ii) the slope of long-term cognitive decline observed in the SAGES I sample as the outcome, and proposed factors that predict complicated delirium as independent variables. Models will be characterized in terms of accuracy

(RMSE), and *r*-squared.

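### NLP delirium terms are chosen in 32 CAM-positive charts on sensitivity alone, so the step that fixes the list for the cohort-wide rate neither measures nor limits false positives

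*Protocol*

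**What the plan says.** Protocol section A.2.7 fixes four things about the NLP project.

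- **Purpose.** The method is to review "medical charts from patients' index hospitalization from both BIDMC and BWH, to determine the rate of delirium".
- **Tuning set.** "We will first conduct a pilot study with N=32 pilot delirium positive cases (by CAM assessment) to test potential delirium terms". No CAM-negative charts are mentioned.
- **Criterion.** The aim is to "narrow the listing to gain high sensitivity (true positive), that is, terms that help us identify who truly has delirium with high frequency".
- **Roll-out.** "Once we identified the search terms with the best sensitivity, we will use NLP with all medical charts of the SAGES I and II cohorts".

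The section adds: "This NLP method will support our chart abstraction procedures described under A.4.10.5". Section A.4.10.5 describes that abstraction as using a standardized form, with development of delirium among the items sought. Section A.3.2, on SAGES I SELECT, says: "Delirium is defined by fulfillment of the Confusion Assessment Method", and then allows chart criteria as an alternative.

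Neither A.2.7 nor the NLP text in section B8 states a specificity, a positive predictive value (PPV), a limit on false positives, a way to handle negated mentions, or a comparison of NLP hits with CAM results.

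**The concern.** The purpose is a rate in whole cohorts, but the list is tuned only on patients known to have delirium. In such a set every hit is a true positive by construction, so neither specificity nor PPV can be estimated. The protocol describes the target as terms that show who truly has delirium. That is a question about PPV, which this pilot cannot answer.

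The selection rule adds to the problem. If a chart is flagged when any listed term occurs, adding a term can never lower sensitivity. A rule that looks only at sensitivity therefore has no ground for rejecting a term that is also common in the notes of non-delirious older surgical patients, or one that appears where a clinician records that delirium was absent.

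What is at stake is chiefly the NLP rate itself. When most patients do not have the condition, a modest false-positive proportion adds many false cases.

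**Working it through.** **Inputs**

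- True delirium rate p = 24% (B.1.3, Project 4 Aim 3a, for SAGES II). SAGES I agrees: 134 delirious of 560 (Project 4 Aim 2c), and 134/560 = 23.9%.
- Maximum number of charts: 560 + 460 = 1,020, before the restriction to participants who consented to chart abstraction.
- Pilot size: 32, all CAM-positive (A.2.7).
- Sensitivity (Se) and specificity (Sp): given nowhere, so both are assumed over a range.

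The protocol states no accuracy or precision figure for the NLP project, so there is none to reproduce.

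**Step 1: apparent rate and PPV**

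Apparent rate = Se × p + (1 − Sp) × (1 − p). PPV = Se × p / apparent rate. False positives = 1,020 × 0.76 × (1 − Sp).

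Example with Se 95% and Sp 90%: 0.95 × 0.24 + 0.10 × 0.76 = 0.228 + 0.076 = 0.304, and PPV = 0.228/0.304 = 0.75.

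| Se | Sp | Apparent rate | PPV | False positives in 1,020 |
|---|---|---|---|---|
| 95% | 98% | 24.3% | 0.94 | 16 |
| 95% | 95% | 26.6% | 0.86 | 39 |
| 95% | 90% | 30.4% | 0.75 | 78 |
| 95% | 80% | 38.0% | 0.60 | 155 |
| 95% | 70% | 45.6% | 0.50 | 233 |
| 90% | 98% | 23.1% | 0.93 | 16 |
| 90% | 95% | 25.4% | 0.85 | 39 |
| 70% | 95% | 20.6% | 0.82 | 39 |

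**Step 2: break-even specificity**

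Setting the apparent rate equal to p gives Sp = 1 − (1 − Se) × p/(1 − p), with p/(1 − p) = 0.24/0.76 = 0.316.

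- Se 95%: 1 − 0.05 × 0.316 = 98.4%
- Se 90%: 1 − 0.10 × 0.316 = 96.8%
- Se 80%: 93.7%
- Se 70%: 90.5%

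Below these values the rate is overstated, and above them it is understated. The higher the sensitivity achieved, the higher the specificity needed.

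**Step 3: what the pilot can estimate**

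Exact (Clopper-Pearson) 95% intervals for sensitivity are 89.1% to 100% if 32 of 32 charts are found, and 79.2% to 99.2% if 30 of 32 are found. Both are optimistic, because the terms are chosen and assessed in the same charts. With no CAM-negative charts, the pilot gives no estimate of specificity at all.

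**The case against.** **Accuracy can be worked out later.** The full run covers all charts, most of them from non-delirious patients. SAGES II patients have daily CAM interviews (A.4.9), and SAGES I incident delirium is listed as CAM-assessed (Table 2). Specificity and PPV could therefore be computed afterwards, and such metrics are often left to an analysis plan. This stands as far as it goes: the pilot cannot give specificity, but the wider data could. It does not repair the selection rule, which the protocol does state and which fixes the list before any false positive can be seen.

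**NLP only supports abstraction.** A sensitive first pass followed by structured review is a legitimate design, and favouring sensitivity would be reasonable there. But the protocol does not say that an abstractor confirms each hit before it counts, and it gives the rate itself as the purpose.

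**The list is to be narrowed.** Dropping terms cannot raise the sensitivity of an any-term list, so some selectivity seems intended. No criterion for it is given.

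**Two stronger readings go too far.** A reader might infer that the NLP rate is inflated. The documents do not show this: Se 95% with Sp 98% gives almost no bias, and Se 70% with Sp 95% understates the rate. A reader might also infer that false positives contaminate the delirium variable in all five projects. No section says that NLP output sets delirium status, and NLP appears in neither the aims, the power section nor the analyses by project. The CAM-or-chart definition makes a route possible but does not establish one.

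**Conclusion.** The design point holds. The term list is selected in a way that cannot see false positives, and it is then used to produce a rate in cohorts where about three quarters of patients are non-delirious. At p = 24%, the rate is overstated unless specificity is about 97% or more at sensitivity 90%, or 98.4% at sensitivity 95%. Overstatement is the likelier direction if the high sensitivity sought is reached, but neither direction nor size is known. The table rests on assumed values of Se and Sp and on CAM as the reference.

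This is a flaw in an ancillary measure that should be corrected before the list is fixed. It is not shown to affect the main inferences of Projects 1 to 5.

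**What to change.** Amend A.2.7 as follows.

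1. Add CAM-negative index charts to the pilot. Project 4 Aim 1b counts 90 + 44 = 134 delirious and 285 + 141 = 426 non-delirious SAGES I participants ("the remaining 44 delirious and 141 nondelirious SAGES I participants will constitute the model testing sample"), so charts are available. Classify them by CAM result alone. The 134 may include chart-defined cases, and using those to judge a chart-reading tool would be circular.
2. Choose terms on sensitivity and specificity jointly, with negation handling, and then lock the list.
3. Report sensitivity, specificity and PPV against CAM in charts not used for tuning. Size that set deliberately: 95 of 100 CAM-negative charts correct gives an exact 95% interval for specificity of 88.7% to 98.4%, which still contains the 96.8% break-even, and 29 of 32 gives 75.0% to 98.0%.
4. Either confirm NLP hits through the existing chart abstraction before they count, or report the rate with the error rates taken into account, for example (apparent rate + Sp − 1)/(Se + Sp − 1). With the Se 95%, Sp 90% example this returns (0.304 − 0.10)/0.85 = 0.24.
5. State whether NLP hits can change a participant's delirium status.

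The cost is a modest number of extra, already-consented charts in the pilot and a somewhat lower sensitivity than a sensitivity-only list would show.

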A.3.1. SAGES I Cohort (N=560): Eligibility criteria included for initial enrollment: 1) age 70 years and older; 2) English speaking; 3) scheduled to undergo elective surgery; 4) scheduled at least 6 days prior to surgery to allow adequate time for the baseline assessment; 5) anticipated length of stay of at least 2 days; 6) planned general or regional anesthesia; and 7) living within 40 miles from study site. Eligible surgical procedures were: total hip or knee replacement, lumbar, cervical, or sacral laminectomy, lower extremity arterial bypass surgery, open abdominal aortic aneurysm repair, or colectomy. Exclusion criteria included: 1) evidence of dementia (dementia diagnosis, use of dementia drugs, or score <69 or education-adjusted equivalent on baseline Modified Mini-Mental State Test⁵³ 2) active delirium on initial cognitive testing: 3) hospitalization within 3 months prior to enrollment to minimize risk of recent delirium; 4) terminal condition with life expectancy < 6 months including terminal diagnoses such as metastatic cancer, pancreatic cancer, or receiving palliative care; 5) inability to perform cognitive tests due to legal blindness or severe deafness; 6) history of schizophrenia or psychosis; 7) current chemotherapy due to patient time burden; 8) documented history of alcohol abuse or withdrawal within last 6 months, and/or reporting more than 5 (4) drinks per day for men (women); 9) and inability to pass an assessment for capacity to provide informed consent. Initially 560 patients were enrolled; 6 patients were excluded due to baseline dementia. We will continue follow-up interviews with this cohort under the existing IRB protocol (2009P-000262).

A.3.2. SAGES I SELECT Sample Sub-group (N=148). A subset of selected participants from SAGES I will be invited to participate in lumbar puncture or amyloid-PET, MRI and Transcranial Magnetic Stimulation (TMS) procedures based on their delirium status. Delirium is defined by fulfillment of the Confusion Assessment Method¹ or chart criteria.⁵⁴ We will invite all SAGES I participants who developed delirium during the index hospitalization to participate, and we will enroll 74 participants into this subgroup. Next, we will enroll a sample of 74 patients who did not develop delirium or sub-

syndromal delirium in the index or subsequent hospitalizations, using a probability sampling approach to generate a frequency-matched comparison group with a comparable distribution of baseline General Cognitive Performance (GCP)⁵⁵, age, and their interaction. This SAGES I SELECT subgroup (N=148) will undergo additional procedures, including a lumbar puncture (LP), phlebotomy, PET, MRI and Transcranial Magnetic Stimulation (TMS) described in section C below. All procedures will take place one time only except for TMS which will be offered up to 3 times in selected patients.

A.3.2.1 Setting and Methods: The MRI procedures will be performed on one of the whole body scanners located on the East Campus of the Beth Israel Deaconess Medical Center or at the 1.5 Tesla or 3.0 Tesla GE scanners at the BIDMC East and West Campus. This study will use a 3.0 Tesla scanner that has dedicated time for research-related imaging under the direction of [name] and his study team. The PET procedure will also be performed at the BIDMC Division of Nuclear Medicine and Molecular Imaging (NMMI) on a Siemens Biograph m64 time-of-flight PET/CT scanner by the NMMI team. PET and MRI data will be analyzed at BIDMC, BWH, and at MGH under the direction of [name]. The EEG, TMS procedures, LP/CSF collection, and phlebotomy of this study will be conducted under the direction of [name] and his study team. Blood will be collected in patients' homes or at the CRC. The LP will be conducted at the BIDMC CRC under the direction of [name], a BIDMC neurologist. The laboratory testing for inflammatory biomarkers, will be conducted in the laboratory of Drs. [name]/[name] at BIDMC and [name] at MGH.

SAGES I full cohort participants, who are eligible and who indicated interest in continued study participation during a follow-up interview of the initial SAGES I study, will be called by a coordinator to schedule a visit to the BIDMC Research MRI and Clinical Research Center (CRC) for LP, phlebotomy, MRI, and TMS-EEG. SAGES I Select participants who are ineligible for LP will be invited to participate in amyloid-PET imaging instead. Only patients who provide written or verbal consent and who demonstrated capacity to consent by SAGES procedures will be enrolled into this study. The consent will be administered by study staff. All participants will undergo separate eligibility assessments for each procedure (section C).

A.3.2.2. Phlebotomy: During phlebotomy, in total less than 40mL will be collected at two different occasions. To assess LP eligibility (platelet count and INR), <10 mL blood will be drawn in 2 different tubes (~4mL in lavender top and ~3mL in light blue top) in participants' home. An additional 30 ml (three 10 mL heparin tubes) will be collected at the CRC, centrifuged to separate plasma from cellular material, divided into small samples, and frozen at -80C for future use. Blood will be stored in the SAGES freezer. Blood samples will be collected via peripheral venipuncture into sterile vacuum tubes using either a vacutainer or butterfly system. The first draw of blood will be collected in patients' homes by trained and experienced research staff or by a phlebotomy service affiliated with Hebrew SeniorLife. The second draw will be collected in the BIDMC CRC (at the same day as the LP or MRI) by nursing staff. Each procedure will last about 10 minutes. For the first blood draw hemolysis is not a concern and therefore the blood can be drawn in participant's homes. For the second blood draw immediate processing after the draw is essential and therefor the blood needs to be drawn at the CRC.

A.3.2.3. Lumbar Puncture (LP): During LP, 10-15 cc of CSF will be collected and centrifuged at low speed to remove any cellular contaminants, divided into aliquots and frozen in 0.5 ml polypropylene cryotubes for inflammatory and AD biomarkers. CSF will be stored at -80°C. The LP procedure, including consent, will take about 1-2 hours, and will be performed by one of the study Neurologists under supervision of [name] and with assistance from the CRC nurses as needed. During the LP, participants are placed in a left lateral position, with the back flexed, and knees are drawn up towards the chest, or sitting up and bent forward, whichever is easier for the participant. The lumbar region of the back will be cleaned with betadine, twice. Lidocaine 1% will be injected into the subcutaneous area between the L3-4 or L4-5 spinous process. Once the area is numb, a 24G or 25G atraumatic Sprotte LP needle will be placed and CSF will be collected. To clear any blood from minor

trauma associated with needle insertion, the first 1-2 ml of CSF are discarded (or more if needed) to eliminate blood. Participants will remain in the clinic for about 15-30 minutes for monitoring after the procedure. They will be given the option to have something to eat or drink before they leave. They will be advised to not do any strenuous physical activity for the next 24 hours, including lifting, bending, doing housework and gardening, or doing exercise such as jogging or bicycle riding. Before participants leave, they will be asked about how they are feeling and given a short questionnaire asking about their experience with the LP. One day after the LP, a member of the research team will call the participant to ask about how s/he is feeling.

A.3.2.4. MRI: Participants will complete a structural Magnetic Resonance Imaging (MRI) scan in the 1.5T or 3T scanner. Upon screening with the MRI team, if a participant indicates they had an injury to the eye involving metal or has potentially contraindicated metallic implants without previous x-ray exams, an orbital or body x-ray may be indicated prior to the MRI to rule out metal objects in the body. The MRI scanning procedures will take approximately 1-1½ hours. During the scan the participant will lie on his/her back in the scanner with their head inside an imaging coil. Special pillows will be used to hold their head securely in place. Ear plugs will be provided to the subject and a pneumatic squeeze ball that triggers an alert at the scanner console when squeezed will be provided. The patient will be able to communicate with the MRI technologists at all times during the exam.

The structural MRI images will be obtained; this takes about 20-30 minutes. The structural MRI images will be used to accurately identify the regions of interest (ROI) for the TMS-EEG procedures.

A.3.2.5. PET: PET scans will take place under supervision of the NMMI faculty and staff. At the beginning of the session, an intravenous catheter will be placed in the antecubital vein of the left arm to participants prepositioned in the bed of the PET scanner or in an adjacent room prior to the scan. This will be used to inject the F¹⁸ Florbetapir radiotracer as a slow intravenous bolus (up to 15 mCi will be administered). The catheter will be removed after the injection. The catheter will be placed by and accessed by a certified nuclear medicine technician. F¹⁸ Florbetapir PET will be acquired with an 370 MBq (10.0 mCi) \pm 10% bolus injection followed by 20 min (4X5min frames) acquisition at 50-70 min post-injection as in the acquisition protocols used in ADNI (ADNI 3). Participants are scanned on a Siemens Biograph m64 time-of-flight PET/CT. Subjects will be instructed to remain still, with eyes open or closed depending on the scan sequence, for the total duration of the scan. The duration of the visit itself will be approximately 2-3 hours (consent, preparation, injection, and 20 min of scanning starting at 50 min after injection.

If a participant wants results of their PET scan released to their physician, they may request it. [name] will communicate with the BIDMC Department of Nuclear Medicine who will access the database and release an unblinded report to [name] and to the OMR. [name] will relay the report and information to the patient's physician, and alert them also that the report and scan can be obtained through the BIDMC Medical Records department. Thus, the report and scan should be accessible through regular channels by all physicians both within and outside the BIDMC system.

A.3.2.6. TMS-EEG: These procedures will take about 4-5 hours. All SAGES I SELECT participants will undergo the first TMS-EEG visit with theta burst stimulation targeted at one of the brain regions identified above (section A.2.5 Project 5) and following procedures as described above. We will then invite all participants back for a second and third time to target the theta burst at the other 2 brain regions within a 6-week timespan after the initial TMS-EEG session.

TMS-EEG Procedures (SAGES I SELECT and SAGES II cohorts):

EEG: A special cap with electrodes is placed on the participant's head. Saline gel will be used to increase electrical conductivity between the electrodes and the scalp. These electrodes will measure electrical activity in the brain; the cap will remain on the patient's head for the duration of the visit. We

will utilize the structural MRI previously acquired in the original SAGES study or will use a standard 10-20 or 10-5 EEG set-up and a standard brain model to ensure correct placement of the TMS coil and EEG electrodes.

TMS: The participant will be seated in a chair and the research team will place the TMS coil against the head. The coil produces a magnetic field that will briefly affect brain function. Target Regions: All subjects will receive single-pulse TMS to up to three cortical regions. The target regions will be the left dorsolateral prefrontal cortex (DLPFC), left inferior parietal lobe (IPL), and left primary motor cortex (M1).

- Determination of Resting Motor Threshold: Resting motor threshold (RMT) will be determined by applying single pulses to the motor region (M1). RMT will be defined as the minimum stimulus intensity that produced a small motor evoked potential (MEP) in the hand musclesabout 50 µV in 50% of 10 trials - as measured by electromyography (EMG) during relaxation of the tested muscles. RMT will be used to guide intensity to be used for single pulse stimulations.
- Baseline Single Pulse TMS: Single-pulse TMS will be applied to the target regions at 110% 130% motor threshold and with an inter-pulse interval between 2-6 seconds to establish the baseline TMS-evoked EEG response and to assess cortical excitability.
 Baseline Paired-Pulse TMS: Pairs of TMS pulses with an inter-pulse interval of 100 ms at 110% 130% motor threshold will be applied to the target regions, and with 2-6 seconds between pulse pairs, to obtain baseline TMS-EEG measures of cortical inhibitory control.
- Determination of Active Motor Threshold (AMT): AMT will be defined as the minimum stimulus intensity that produces a small MEP (about 200 µV in 50% of 10 trials) during isometric contraction of the tested muscles, at about 20% of maximum voluntary contraction while applying single TMS pulses over M1. AMT will be used to determine the intensity for TBS.
- Theta Burst Stimulation (TBS): SAGES II Subjects will receive TBS to M1 (all 3 visits) and SAGES I SELECT subjects will receive TBS to one of the three defined regions (left dorsolateral prefrontal cortex (DLPFC), left inferior parietal lobe (IPL), or left primary motor cortex (M1)), one at each visit. TBS will consist of bursts of 3 pulses at 50 Hz repeated at intervals of 200 ms. Stimulation intensity will be delivered at 80% of active MT (AMT). Corticospinal excitability will be assessed prior to and following theta burst stimulation by measuring peak-to-peak amplitude of MEPs in response to single pulse TMS. MEPs will be recorded prior to TBS and used as a baseline. Following TBS, batches of MEPs will be measured at five, ten, or 15-minute intervals for up to 2 hours to track changes in amplitude over time.

A.4. The SAGES II cohort and procedures specific to the SAGES II cohort

SAGES II Cohort (N=460), will be newly enrolled surgical patients undergoing scheduled eligible surgeries with spinal or general anesthesia at two academic medical centers, Beth Israel Deaconess Medical Center (BIDMC) and Brigham and Women's Hospital (BWH and BWH Faulkner, the same centers where SAGES I and RISE occurred) and followed prospectively at 1, 2, 6, 12, 18, 24 and 36 months. The enrollment age for this cohort will be 65 years and above. Except for age at enrollment, inclusion and exclusion criteria are the same as for the original SAGES I cohort (N=560) outlined above except SAGES II will be enriched with 15% patients with Mild Cognitive Impairment-Amnestic type (MCI-A) identified at baseline in order to examine the impact of delirium in this high-risk group. In a addition to the surgery types listed under SAGES I we will also enroll patients with the following planned surgeries: POPLITEAL, AMPUTATION BELOW AND ABOVE KNEE, PERIPHERAL ARTERY REPAIR OPEN, COLECTOMY LAPAROSCOPIC AND OPEN, BOWEL RESECTION, LUMBAR LAMINECTOMY/FUSION, PANCREATECTOMY, RESECTION

GASTROINTESTINAL MASS, HEPATECTOMY, GASTRECTOMY LAPAROSCOPIC, BOWEL RESECTION LAPAROSCOPIC, ROUX-EN-Y HEPATICOJEJUNOSTOMY, NEPHRECTOMY, laparoscopic, PROSTATECTOMY, laparoscopic, CYSTECTOMY, laparoscopic, NEPHRECTOMY, open. Most Pls and staff members were part of the SAGES I cohort creation and are very familiar with all procedures. We have already successfully pilot-tested all study procedures that we will use for SAGES II (BIDMC IRB protocol #2015 P000273 and PARTNERS IRB protocol # 2017P000064).

SAGES II Sub-group (N=180). This subgroup will meet the same general inclusion and exclusion criteria as all SAGES II patients, will be selected based on their baseline neuropsychological testing and undergo the same specialized procedures as the SAGES I SELECT cohort (except excluding lumbar puncture), including, magnetic resonance imaging (MRI) scans and electroencephalogram (EEG) with non-invasive transcranial magnetic stimulation (TMS). Prior to the procedures subjects must complete a screening form designed to identify any contraindications.

A.4.1. Setting and Methods: The study procedures, including screening, baseline, hospital, and followup assessments are detailed below. PET, MRI and TMS-EEG procedures will take place at the same locations under the supervision of the same persons outlined above (Section A.3.2.1). All face-to-face assessments will be conducted either in the subject's place of residence (in-person or remotely via telephone or videoconference using an IRB approved platform like zoom or Starleaf---once proper agreements specific to Zoom are in place), at Hebrew SeniorLife, or in the out-patient clinics according to the convenience and preference of the subject. Patients will be identified from the BIDMC or BWH (including BWH Faulkner) operating room advanced booking schedule and will be approached and enrolled (after permission from their surgeons) in either the subject's choice of their home or during an office visit. We plan to enroll 230 subjects per year. Based on our previous studies, we anticipate that about 500 surgical patients per year will meet our eligibility criteria across the 2 sites and will be available for the study, yielding an eligible-to-enroll ratio of 2.2:1. Thus, we anticipate that we will have adequate availability of patients to conduct the study.

A.4.2. Research staff: All research staff, comprised of experienced clinical research interviewers, will undergo intensive training, following standardized procedures, in all questionnaires and research methods. They will be carefully trained to handle emergency issues in the home setting, and the Project and Core leaders will be available to provide back-up at all times. Baseline standardization and inter-rater reliability assessments will be conducted to verify consistency of all staff on the primary outcomes (including the neuropsychological test battery and functional outcomes), as well as key risk factor variables (including the delirium assessment). Interviewer quality checks with inter-rater reliability assessments on all key study variables will be performed every 6 months for the duration of the study. All staff will undergo training on infection control and proper use of personal protective equipment (PPE). All staff will continue to be compliant with BIDMC, BWH/BWFH, and Hebrew SeniorLife guidance on interacting with study participants and patients, and will undergo daily symptom screening during the COVID19 crisis.

For the in-person assessments, both the study team member and the study participant will wear face masks and face shields at all times. For the timed walk, to ensure participant safety, study staff will walk behind participant during assessment. For the grip strength test, participant will be handed a sanitized dynamometer. Both the study team member and the study participant will perform hand hygiene and wear gloves before handling the dynamometer. After the assessment, both will remove their gloves and perform hand hygiene again.

For all procedures conducted at the BIDMC, staff will follow standard BIDMC COVID-19 guidelines.

A.4.3. Screening assessment (n=460 entire SAGES II cohort): The purpose of the screening assessment is to verify subject eligibility. Based on a 10-minute patient interview along with medical record review, information will be collected to establish eligibility criteria and to rule out the presence of

delirium at baseline. The interview will include: digit span, Confusion Assessment Method (CAM), Delirium Symptom Interview (DSI), the Montreal Cognitive Assessment Test (MoCa). Patients with a positive CAM and/or a MoCA score under 20 will be adjudicated by [name]. The screening will also complete the first stage of our two-stage process to identify patients' cognitive status. Patients with Mild Cognitive Impairment-Amnestic type (MCI-A) will be eligible but patients with dementia will be excluded. All screening information will be entered into an iPad or tablet computer by the interviewer, and immediate subject eligibility will be determined based on internal algorithms to determine all inclusion and exclusion criteria and to rule out delirium and dementia. The baseline assessment will take place based on participant's preference in their home, at HSL or BIDMC or any other place determined by the participant.

A.4.4. Baseline assessment interviews (n=460 entire SAGES II cohort): The purposes of the baseline assessment are to characterize the subjects, to document baseline neurocognitive function, to characterize baseline risk factors for delirium and cognitive decline, and to measure potentially confounding factors. This assessment will be conducted immediately following the screening assessment in eligible patients. The 80-minute baseline interview will collect information on cognitive functioning (neuropsychological test battery, Table 5), demographics, education, occupation, medical diagnoses, comorbidity, medications, health habits (e.g., smoking, alcohol), hearing, mobility, basic and instrumental activities of daily living, physical functioning, depression, and anxiety. A family or caregiver interview will be conducted (in-person or over the phone, or if both is not possible we will mail the questionnaire with a pre-stamped return envelope) to establish the subject's baseline cognitive functioning, to assess for evidence of dementia, and to determine any recent changes in mental status. Based on our previous studies, about 3-4% of participants will not have a family member or caregiver available to participate in these interviews; in these cases, we will approach (with the patient's consent) friends, neighbors, visiting nurses, or other reporters about the patient's baseline functioning. All enrollment and baseline assessments will be completed prior to the scheduled surgical admission.

Table 5. Description of the SAGES Neuropsychological Battery to assess cognitive functioning							
Test	Description	Domain(s) tested					
Trail-making Tests A and B	Participant must connect a sequence of alternating numbers and letters	Executive function, visual spatial function, processing speed					
Phonemic F-A-S Fluency	Participant must generate as many words in one minute as possible beginning with a given letter over three trials	Executive function, semantic memory, language					
Category Fluency	Participant must generate as many words in one minute as possible from a semantic category (e.g., "animals")	Executive function, semantic memory, language					
Visual Search and Attention Test	Four timed visual cancellation tasks where participant must cross out letters and symbols identical to a target	Executive, visual spatial function					
Hopkins Verbal Learning Test - Revised (HVLT-R)	A list of words is read to the participant, who is asked to repeat the list back over multiple learning and delayed recall trials	Verbal episodic memory					
Digit Span Forward/Backward	Participant is asked to repeat a string of digits forward and in reverse order	Sustained attention					
Boston Naming Test	Participant is presented with drawings of common objects, which then must be named correctly	Confrontation naming, language					
RBANS Digit Symbol Substitution	Using a key provided, the participant matches symbols to numbers as quickly as possible while being timed	Executive function, visual spatial function, processing speed					
AmNART	Participant is asked to pronounced words aloud presented to them on a piece of paper	Verbal IQ					

RBANS = Repeatable Battery for the Assessment of Neuropsychological Status AmNART = American National Adult Reading Test

A.4.5. Blood: (n=460 entire SAGES II cohort): We will collect blood from the entire SAGES II cohort participants at 4 time points: at the time of the baseline study assessment (baseline), on postoperative days 1, and 2 (POD1, POD2) and 1 month after surgery (100 ml total over 6 weeks). If a patient is discharged on the day of surgery, we will obtain blood on POD 1 or POD 2 in patient's discharge location. During the baseline and POD1 (or POD 0) assessments, three green top tubes (30 cc) will be

